- (1) Non-office work: Workers normally carry out their jobs with a range of environment in an indoor or outdoor working space where close contact with the general public is frequent, and thus non-office work settings are considered at a higher risk of COVID-19 than the office work settings. Workers in non-office settings mainly include construction, accommodation and food service (e.g., hotel, restaurant), art/entertainment and recreation, professional bus drivers, outdoor instructor, real estate, wholesale and retail trades, etc.
- (2) Mobile work: Workers who frequently move within or in and out of Hong Kong for conducting business that involves closer and more frequent contact with the general public than the non-office workers, thus their risks to contracting COVID-19 are regarded to be the highest among 3 selected work settings. Workers in mobile work settings mainly include taxi drivers, food delivery workers, courier delivery workers, police officer, etc.
- (3) Office work: Workers normally carry out professional duties and administrative work in an indoor working space, such as an office or a room. Although the details of the job nature depend on the type of business to be involved, office work usually include using computers, communicating with others by telephone or fax, keeping records and files, etc. In general, office work offers relatively stable working environment where close contact with the general public is less frequent, and thus is considered having a low risk of contracting COVID-19 in the workplace. Workers in office work setting mainly include clerical workers, administrative workers, computer technicians, information and communication workers, etc.

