**Sample size:** We estimated sample size for the Part I – Randomized controlled trial according to two independent proportions power analysis. As there is no relevant data of willingness to vaccination on our target subjects to guide the sample size calculation regarding an educational intervention against COVID-19, we employed a conservative assumption that the intervention will make a 20% change for worker's attitude to vaccination/virus test, sample size for both groups/arms will be 124, 130, 124, 109 and 79 for the proportion of willingness to vaccination/virus test of 30%, 40%, 50%, 60%, and 70%, respectively, with a 90% G-power. Therefore, a minimal 79 pairs subjects are required to achieve the primary objective (RCT) of this proposal project; if further assuming a loss-to-follow-up rate of about 40%, then an overall 222 participants with 111 subjects in the intervention group and 111 subjects in the control group are required. However, if given the most conservative sample size estimation with 40% loss-to-

follow-up rate, a total of 364 subjects with 182 subjects in each arm of RCT ( $130*1.4$ ) are required. Therefore, the overall sample size for RCT could reasonably range from 222 to 364 to satisfy the primary research objective of this proposal project. In the proposed RCT, we considered taking the mean of the “most-least conservative” sample sizes of 294 [ $(222+364)/2$ ] from G-power as a reasonable sample size with 147 subjects in each arm, and this sample size (i.e., 294) has already taken into consideration a potential loss-to-follow-up rate of about 40%.

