### *(iii.1) Procedure of Part I study*

**Part I** is a 9-month **randomized controlled trial** to be conducted with single blinding and concealment during Year 1-2 (as shown in **Figure 1**).

**Study subjects of the RCT:** Two hundred ninety four workers from non-office, mobile and office work settings will be invited to participate in the RCT. The aim of the RCT is to test the hypothesis that a 9-month intervention program improves primarily the attitude towards vaccination and COVID-19 testing, with impact on the improving the actual uptake of COVID-19 testing and risk profile toward outbreaks at workplace.

**Procedures of the RCT:** All 294 participants will be randomized to intervention group and control group. Intervention group will receive theory-based educational intervention using the Theory of Planned Behaviours (TPB) PLUS general health information, while the control group will receive only general health information. As this RCT will investigate factors that can explain worker's intention to vaccination and virus testing, the theoretical framework using the theory for planned behavior (i.e., TPB) is a proper approach for improving workers' attitude toward SARS-CoV-2 and raise their intention to vaccination and virus testing. The intervention will be implemented at the baseline with measurements repeated at the 3rd month, 6th month and 9th month. The standardized mode of intervention includes face-to-face/online seminar (depends on the COVID-19 situation), message via mobile phone, promotion pamphlet, etc.

Primary outcomes of the RCT include attitude to vaccination and virus testing, and the secondary outcomes of the RCT are actual uptakes of virus antibody testing and changes of risk profile toward outbreaks in the workplace.

Key contents of intervention would include:

- TPB intervention: building positive attitudes towards COVID-19 related preventive behaviour (e.g., good compliance with infection control measures, encouraging uptake of testing and vaccination), subjective norms (tackling strategies for perceived social pressure from others or normative beliefs), and improving perceived behavioural control towards risks of outbreaks in workplace.
- Other necessary information: basic knowledge of SARS-CoV-2, chain of infection, health and social consequences of infection, general infection control measures, workplace engineering and administrative control measures.

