### **(iv) Data processing & analysis**

For quantitative results, descriptive analysis and Chi-square will be used for baseline data to analyse the difference in exposure and prevention, willingness to vaccination/testing and actual uptake of tests between comparison groups (e.g., work settings). Paired t-test and covariance analysis will be performed to compare the longitudinal changes of scores of each exposure prevention behaviour factors, attitude and willingness to vaccination and virus testing over time. Structural equation modelling and multivariate regression logistic modelling will be used to analyze the structural relationship between measured variables and latent constructs, as well as examine the association of exposure profile with willingness to vaccination/testing or uptake testing. Effectiveness of intervention will be examined by multivariable linear (for continuous nature of outcome) or Cox proportional hazard models (for binary outcome). Loss-to-follow-up will be reported and intention-to-treat analysis will be used for addressing the loss-to-follow-

up issue of the RCT. All statistical analyses for longitudinal quantitative and RCT data will be conducted by SPSS Version 26 and/or SAS 9.4 (SAS Institute Inc., North Carolina). P-value of less than 0.05 is considered statistically significant.

For qualitative analysis, the tape-recorded individual interviews will be transcribed verbatim and thematically analysed using Grounded Theory approach. Data will be horizontally compared between participants, and longitudinally analysed, tracking and explaining attitudinal and behavioral changes of individuals across time. The qualitative data will be delineated to a typology of reasons for (1) accepting, delaying or refusal of COVID-19 vaccine, and (2) factors contributing to uptake of COVID-19 testing in the workplace, generated through thematic analysis.

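### The RCT's between-arm attitude analysis is not tied to baseline attitude, work setting or the month 3, 6 and 9 visits, and paired t-tests are not confined to Part II

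*Combined protocol and SAP*

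**What the plan says.** Section (iii.1) describes a 9-month RCT with the intervention delivered at baseline and measurements repeated at months 3, 6 and 9. The primary outcomes are attitude to vaccination and to virus testing. The intervention arm gets theory-based education plus general health information; the control arm gets the general information alone. On allocation the section says "All 294 participants will be randomized to intervention group and control group". It mentions single blinding and concealment, but gives no allocation method and no stratification.

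Section (iv) holds all the quantitative analysis text:

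- On change over time: "Paired t-test and covariance analysis will be performed to compare the longitudinal changes of scores of each exposure prevention behaviour factors". The same sentence extends to attitude and willingness, and does not say whether it covers the RCT, Part II or both.
- On the intervention: "Effectiveness of intervention will be examined by multivariable linear (for continuous nature of outcome) or Cox proportional hazard models (for binary outcome".
- Intention-to-treat analysis is named as the answer to loss to follow-up, and "P-value of less than 0.05 is considered statistically significant".

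The section names no covariate list, baseline term, setting term, mixed model, GEE or primary time point for the RCT.

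Section (ii) ranks the three work settings by infection risk; of mobile workers it says "their risks to contracting COVID-19 are regarded to be the highest among 3 selected work settings". Its sample-size paragraph assumes that "the intervention will make a 20% change for worker's attitude to vaccination/virus test", "with a 90% G-power", allows for about 40% loss, and settles on 147 per arm.

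**The concern.** The trial collects one baseline and three follow-up measurements, but the plan does not say how they enter the comparison of arms. Three things follow.

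- **Inference.** Paired tests are listed for attitude scores without being confined to Part II. A paired test asks whether one group changed. Both arms receive health information and both may change, so a significant result in the intervention arm alone could be mistaken for an intervention effect.
- **Model fit.** Willingness can be gained and lost again, and it is seen only at fixed visits. A Cox model for time to an event suits that poorly.
- **Precision and partial data.** Baseline attitude is likely to be a strong predictor of later attitude. If it is not in the model, the standard error is larger than it need be. If only month 9 is analysed, workers seen at month 3 or 6 and then lost add little. With about 40% loss expected, neither is a small matter.

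**Working it through.** **1. The plan's sample size.** Inputs from section (ii): 20-point difference, 90% power, control rates 30% to 70%. Alpha is 0.05 from section (iv), taken as two-sided.

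n per arm = [1.960·√(2p̄(1−p̄)) + 1.282·√(p₁(1−p₁) + p₂(1−p₂))]² / 0.20²

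| Control rate | Stated | Pooled formula | Arcsine formula |
|---|---|---|---|
| 30% | 124 | 124 | 125 |
| 40% | 130 | 130 | 130 |
| 50% | 124 | 124 | 125 |
| 60% | 109 | 109 | 108 |
| 70% | 79 | 82 | 79 |

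The figures reproduce: four of five exactly by the pooled formula, and all five to within one by the arcsine formula. Multiplying by 1.4 gives 111 and 182 per arm, totals of 222 and 364 and a mean of 293; the plan adopts 294.

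**2. How much precision is left.** 147 × 0.6 ≈ 88 completers per arm. Power for the 20-point difference is then 78%, 76%, 78%, 83% and 92% at control rates of 30%, 40%, 50%, 60% and 70%. Efficiency therefore matters.

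**3. Baseline adjustment at month 9, continuous score.** The documents give no SD, correlation or scale, so the baseline-to-month-9 correlation ρ is an assumption. Relative to an unadjusted month-9 comparison, the variance is 1 − ρ². The difference detectable with 90% power is (1.960 + 1.282)·√(2(1 − ρ²)/88) SD; unadjusted it is 0.49 SD.

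| ρ | 1 − ρ² | SE reduction | Detectable difference |
|---|---|---|---|
| 0.3 | 0.91 | 5% | 0.47 SD |
| 0.5 | 0.75 | 13% | 0.42 SD |
| 0.7 | 0.51 | 29% | 0.35 SD |

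The correlation that counts is the one across the full nine months. If 0.7 held only between adjacent visits and decayed geometrically, ρ would be 0.7³ = 0.343, the variance ratio 0.882 and the SE reduction about 6%.

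**4. What the repeated visits add.** With complete data, a month-9 contrast gains only what step 3 shows. Averaging the three visits with baseline adjustment gives relative variance (1 + 2ρ)/3 − ρ² = 0.443, 0.417 and 0.310 under equal correlations, but that estimates an average effect over months 3 to 9, not a month-9 effect. For month 9, the visits help mainly by bringing in workers with partial follow-up. The documents give no dropout pattern from which to size that.

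**5. Within-arm paired tests.** Assume no intervention effect, both arms drifting by 0.2 SD, ρ = 0.5 and 88 per arm. The SE of the mean change is √(2 × 0.5/88) = 0.107 SD, so each arm's paired test is significant with probability 0.467. The chance that exactly one arm is significant is 2 × 0.467 × 0.533 ≈ 0.50.

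**6. Setting.** Assume equal thirds (294/3 = 98) and, since the documents are silent, simple randomisation. Under Binomial(98, 0.5), a given setting splits 39:59 or more unevenly in 5.4% of trials. The effect on precision cannot be computed, because the documents rank settings by infection risk and not by attitude.

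**The case against.** The strongest reply is that the plan is brief, not wrong, and that several harsher readings go beyond its text.

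- A reader might infer that the models leave out baseline attitude. The documents do not say so. Multivariable implies some covariates, and covariance analysis may well mean ANCOVA with baseline as covariate. If that is meant for the arm comparison, the gain in step 3 is already planned. This stands, and it limits the size of the point.
- A reader might infer that the paired t-test is the effectiveness test. It is not: effectiveness has its own sentence. Paired tests fit Part II, where one baseline and one follow-up survey are compared. What remains is that the sentence names RCT primary outcomes and sets no limit.
- A reader might infer simple randomisation. The text is silent on method.
- It is tempting to value 176 completers as 210 to 345 unadjusted ones (176/0.84 and 176/0.51, for correlations of 0.4 and 0.7). The arithmetic is right, but the comparator is a wholly unadjusted follow-up test that the plan does not name. The trial is also sized on a binary proportion, to which 1 − ρ² does not carry over.
- A Cox model would use earlier visits through event times and censoring, and intention-to-treat analysis is planned. Both are true. Neither makes Cox suitable for a reversible state, and intention-to-treat alone does not say how partial follow-up enters.
- The change is not free. A mixed model relies on data missing at random, and unweighted GEE on a stronger condition.

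**Conclusion.** The point holds as a recommendation. The plan has the data for a baseline-adjusted repeated-measures comparison of arms and does not commit to one, and its Cox option for binary willingness suits the outcome poorly. This is more than missing detail, because a better-suited method is available from measurements and software already planned.

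The size is modest and conditional. For a continuous score, the month-9 standard error falls by about 5% to 29% for an assumed correlation of 0.3 to 0.7, and only if baseline would otherwise be unadjusted. It falls less for a binary outcome. The gain from baseline adjustment is nil if ANCOVA on baseline was already meant for the arm comparison. The further benefit from partial follow-up is real but cannot be sized. Reading within-arm paired tests as an RCT effect would be an error of validity whatever the precision; the documents leave that reading open but do not state it.

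**What to change.** In section (iv), for each primary attitude outcome:

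- State one between-arm model: a linear mixed model for scores; a logistic mixed model or GEE, in place of Cox, for binary willingness.
- Include months 3, 6 and 9, arm by visit, baseline attitude and work setting, with month 9 as the main contrast.
- Use setting as a covariate, not as a basis for separate comparisons. Assuming equal thirds, each setting would have about 29 completers per arm (88/3), and power for 20 points would be 33% to 48%.
- Say that within-arm paired t-tests are not evidence of an RCT effect; keep them for Part II.
- State the missing-data assumption.

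In section (iii.1), state the allocation method and, if not already intended, randomise in blocks within the three settings.

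The cost is analysis wording, three randomisation lists instead of one, and open reliance on missing at random (a stronger condition for unweighted GEE) with about 40% loss. Both named packages, SPSS and SAS, fit these models, and no new data are needed.

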### **(ii) Subjects to be included**

**Study subjects:** In the Part I randomized controlled trial (RCT), 294 eligible workers from 3 non-healthcare work settings will be recruited, and randomized into intervention group (147 subjects) and control group (147 subjects). To be eligible to the Part I RCT, all participants are required to be aged 18 or above, who can read Chinese and currently being employed in three non-healthcare work settings from non-office, mobile, and office work environment in Hong Kong. We attempt to follow-up all participants of the RCT for 9 months to observe the effectiveness of the intervention on improving the primary outcomes, i.e., attitude to vaccination and SARS-CoV-2 testing.

In Part II longitudinal quantitative study, we plan to recruit a total of 1,495 workers who are aged 18 or above and currently working in non-office, mobile, or office work setting in Hong Kong. All eligible study subjects in Part II longitudinal/ prospective cohort study will be recruited in the timeline of 1.5th -3.5th year of the project and followed up for 2 years to observe the changes of attitude to vaccination and virus testing as well as risk profiles of workers towards outbreaks over time.

Figure 1. Workflow chart of hazard identification of outbreaks and control measures in work settings

\* After considering a lost-to-follow-up rate of about 40%

In the Part III longitudinal qualitative study, we plan to recruit an overall 26 management staff and frontline workers (in a ratio of 1:2) with same inclusion/exclusion criteria as the Part I & II study, i.e., aged 18 or above and currently being employed in three non-healthcare work settings from non-office, mobile, and office work environment in Hong Kong.

All above planned number of participants to be enrolled in the baseline of the Part I, II and III study have already considered a potential loss-to-follow-up rate of about 40%.

**Settings:** The 3 work settings are categorized by types as below according to their job nature and working environment:

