### ***(iii.5) SARS-CoV-2 antibody rapid test***

All participants of the RCT who do not finish COVID-19 vaccination will be invited to take the SARS-CoV-2 antibody rapid test four times points during the study to observe their attitudes toward antibody tests and their actual updates of the testing and compare the differences between the intervention and control group, i.e., at baseline, 3rd month, 6th month and 9th month of the RCT. We are also interested in inviting and welcoming those already with complete vaccination to participate in the SARS-CoV-2 antibody rapid test to understand their attitudes towards antibody testing and actual uptakes, and same primary outcomes between the intervention and control arms will be compared. The self-sampling test kit will detect the IgG/IgM antibody of SARS-CoV-2 from whole blood with above 90% sensitivity and specificity, which is recommended by US FDA.

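### Cox regression is specified for yes/no trial outcomes seen only at fixed visits, possibly present at baseline and reversible; it does not target the difference in proportions used for sizing

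*Combined protocol and SAP*

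**What the plan says.** Section (iv), Data processing & analysis, is the only place that says how the effect of the RCT intervention will be tested: "Effectiveness of intervention will be examined by multivariable linear (for continuous nature of outcome) or Cox proportional hazard models (for binary outcome". Logistic modelling appears in that section only for associations between exposure profile and willingness or uptake. The same section plans paired t-tests and covariance analysis to "compare the longitudinal changes of scores of each exposure prevention behaviour factors, attitude and willingness to vaccination and virus testing over time", so attitude and willingness may also be treated as scores. The scale is not defined.

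The passages that determine whether Cox fits are these:

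- **Schedule.** Section (iii.1): "The intervention will be implemented at the baseline with measurements repeated at the" third, sixth and ninth months. Section (ii): "We attempt to follow-up all participants of the RCT for 9 months". No event dates between visits are planned.
- **Test uptake.** Section (iii.1): "the secondary outcomes of the RCT are actual uptakes of virus antibody testing", together with changes in risk profile. Under section (iii.5), RCT participants who have not finished vaccination "will be invited to take the SARS-CoV-2 antibody rapid test four times points during the study", the first of these being baseline. Vaccinated participants are welcome too.
- **Baseline status.** Eligibility in section (ii) does not exclude workers who are already willing, and section (iv) analyses willingness and uptake at baseline.
- **Sizing.** Section (ii) sizes the RCT "according to two independent proportions power analysis", with numbers per arm "for the proportion of willingness to vaccination/virus test of 30%, 40%, 50%, 60%, and 70" per cent, for a 20% change at 90% power.

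**The concern.** A Cox model needs an event, a time origin and a set of people still at risk. The plan gives none of these for its binary outcomes, and the outcomes do not supply them naturally. Willingness is a state: a worker can have it at entry, gain it, and lose it again. It is seen at three follow-up visits, so times are grouped and heavily tied.

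Two readings are possible.

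- **Reading 1, time to first willing visit.** Workers willing at baseline are not at risk and drop out of the comparison, and later reversals are ignored. The hazard ratio then describes who first became willing among those unwilling at entry.
- **Reading 2, one common follow-up time for everyone.** Cox is used as a device to obtain a risk ratio. The result then depends on the tie and variance method, which is not stated.

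The same data could therefore support different conclusions according to choices made after the data are seen. The result may also fail to answer the question for which the trial was sized.

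**Working it through.** **1. The plan's sizing.** For two proportions, two-sided 5%, 90% power:

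n per arm = [1.960·√(2p̄(1−p̄)) + 1.282·√(p1(1−p1)+p2(1−p2))]² / (p2−p1)²

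For 50% vs 70%: (1.960×0.6928 + 1.282×0.6782)² / 0.04 = 2.227² / 0.04 = 124, as stated. The five reference proportions give 124, 130, 124, 109 and 82. The plan states 79 for the last, which the unpooled and arcsine variants give. The trial is thus sized on an absolute 20-point difference; no hazard ratio or event count enters. At 147 per arm without loss, power for 50% vs 70% is 94%.

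**2. Who is at risk under reading 1.** Taking the plan's 30–70% range as baseline willingness (an assumption), the workers excluded are 0.30×294 = 88, 0.50×294 = 147 and 0.70×294 = 206.

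**3. A hand example.** Start both arms at 50% willing and assume fixed chances per three-month interval of gaining or losing willingness.

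- *Equal proportions, unequal hazards.* Control 10% gain and 10% loss; intervention 30% and 30%. Control stays at 0.5×0.9 + 0.5×0.1 = 50% at every visit; intervention stays at 0.5×0.7 + 0.5×0.3 = 50%. Yet among the baseline-unwilling, ever willing is 1−0.9³ = 27% vs 1−0.7³ = 66%. Simulated hazard ratio (Efron) 3.3; with 147 per arm Cox rejects in over 99% of trials, the month-9 comparison in 5%.
- *Unequal proportions, equal hazards.* Both arms gain 20%; control loses 20%, intervention 3.06%. Control stays at 50%; intervention goes 58.5%, 65.0%, 70.0%. The hazard of first willingness is identical, so the hazard ratio is 1. Cox rejects in 5%, the month-9 comparison in 93%.

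Keeping baseline-willing workers in, with time to first willing follow-up visit, gives hazard ratios of 1.35 (54% rejection) and 1.20 (24%). A fixed link exists only if willingness is absent at baseline and permanent once gained: for 50% vs 70%, ln(0.3)/ln(0.5) = 1.74.

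**4. Reading 1 under a second model.** Logistic random intercept (SD 1.5), 50% willing, 147 per arm, 4,000 trials per scenario, Cox among the baseline-unwilling with model standard error. Arm effects on the logit at months 3/6/9: fade 1.2/0.6/0; late 0/0/1.2; sustained 1.2/1.2/1.2, where 1.2 is about 20 points. Loss of 40% is spread evenly over the intervals and is independent of outcome. Percent significant:

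| Scenario | Loss | Cox, Breslow | Cox, Efron | Month-9 proportions |
|---|---|---|---|---|
| Null | none | 2 | 5 | 5 |
| Fade | none | 38 | 64 | 5 |
| Late | none | 7 | 15 | 95 |
| Sustained | none | 76 | 91 | 95 |
| Fade | 40% | 34 | 60 | 5 |
| Late | 40% | 4 | 9 | 79 |
| Sustained | 40% | 63 | 83 | 79 |

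Under the null, 44% of workers counted as a first-willing event were unwilling again at month 9. Varying baseline over 30–70% and intercept SD over 1.0–2.5 without loss, with fade set to +20/+10/0 points and late to 0/0/+20, gave fade 14–62% (Breslow) and 62–81% (Efron), and late 0–26% and 7–33%.

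**5. Reading 2.** With 40% loss, 147×0.6 = 88 per arm. Breslow variance of the log ratio is 1/d1 + 1/d2, where d1 and d2 are the events in each arm; the robust variance subtracts 2/n. For 50% vs 70%: d1 = 44, d2 = 61.6, ln(1.4) = 0.3365. Breslow SE = √(1/44 + 1/61.6) = 0.197; robust SE = √(0.03896 − 2/88) = 0.127. The robust SE approximates the true spread, so Breslow power is P[Z > (1.96×0.197 − 0.3365)/0.127] = P[Z > 0.40] = 0.35; simulation gives 34%. Simulated power (%) for +20 points, 5,000 trials per cell:

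| Reference | Breslow | Efron | Robust SE | Two proportions |
|---|---|---|---|---|
| 30% | 58 | 77 | 77 | 79 |
| 40% | 43 | 73 | 74 | 77 |
| 50% | 34 | 75 | 78 | 79 |
| 60% | 24 | 80 | 83 | 84 |
| 70% | 14 | 90 | 93 | 93 |

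Type I error: Breslow 0–1.9%, Efron 3.5–4.5%.

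**6. Test uptake.** Because the test is also offered at baseline, first uptake can fall at time zero. The plan does not say how such workers are handled.

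**The case against.** - *Reach.* The primary outcomes are attitudes, and section (iv) speaks of scores. If they are scored, the linear model applies and secondary test uptake is the clear remaining candidate. This stands as a limit. But the sizing is in proportions willing, the scale is undefined, and binary outcomes are expressly sent to Cox.
- *Neither reading is written in the plan.* True. Excluding baseline-willing workers is an inference from how Cox works, and the sizing proportions are not stated to be baseline prevalences.
- *The late scenario is extreme*, since the intervention starts at baseline. Fair. An effect growing steadily to the same month-9 value (0.4/0.8/1.2 on the logit) is milder, but still gave Breslow 30% and Efron 48% against 95%.
- *A positive result in the fade scenario is not a false positive*, because the effect at months 3 and 6 is real and the plan does not name month 9 as its target. That stands. Reading 1 keeps its type I error, and with a sustained effect and 40% loss Efron Cox (83%) was no weaker than month-9 proportions (79%). The complaint is a different and undeclared target, not invalidity.
- *Common-time Cox with robust variance is nearly a modified-Poisson analysis.* Correct, and the table for reading 2 supports it. The plan does not state it, however, and Breslow with the model standard error is far weaker.
- *Logistic and modified-Poisson models also estimate ratios.* True. The mismatch with sizing matters chiefly under reading 1, where the same 20 points can correspond to a hazard ratio of 1. Reporting a risk difference settles the remainder.

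**Conclusion.** The concern holds and should be fixed before analysis. As written, the binary-outcome analysis is not defined well enough to be carried out in only one way. On its most natural reading it targets first willingness among the baseline-unwilling, not the difference in proportions behind the sample size. It can be positive when the arms are equal at month 9 (38% or 64% of simulated trials, against 5%) and negative when they differ there by about 20 points (significant in only 7% or 15%, against 95%). On the common-time reading, at a 50% reference and 88 per arm, power runs from 34% to 78% according to an unstated tie or variance choice.

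The size rests on assumed effect patterns, correlation over time, baseline willingness and loss; the documents give none of the patterns. Confidence is high that the specification does not fit the outcomes. How far the primary outcomes are affected depends on whether they are analysed as yes/no.

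**What to change.** In section (iv), replace the Cox clause for binary outcomes along these lines:

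> Binary RCT outcomes will be compared between arms at month 9 with a logistic or modified-Poisson model with robust standard errors, adjusted for baseline status and work setting. The risk difference will be reported with its 95% confidence interval.

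A GEE or mixed logistic model over months 3, 6 and 9, with arm, visit and arm-by-visit terms, is an equally good choice; select one in advance. Also:

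- state which outcomes are yes/no and which are scores;
- name one primary time point. Month 9, the end of follow-up, is the natural candidate, but the plan names none;
- if time to first test uptake is wanted, keep it as a secondary discrete-time analysis over the offered visits and say how baseline uptake is handled;
- if Cox is kept for any outcome, state the event, time origin, risk set and tie or variance method.

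The cost is two or three sentences. No new data are needed, and the methods are standard in the SPSS and SAS versions already named. In 600 simulated trials per scenario with 40% loss, the baseline-adjusted GEE contrast at month 9 rejected in 82% (sustained), 83% (late) and 6% (faded); baseline-adjusted month-9 logistic regression gave 81%, 80% and 7%. No material power is lost.

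### The plan does not say how workers lost to follow-up count in the antibody-test uptake analysis, and a default Cox model would leave an arm difference in drop-out out of the result

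*Combined protocol and SAP*

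**What the plan says.** Section (iii.1) names the outcome: "the secondary outcomes of the RCT are actual uptakes of virus antibody testing", alongside changes in risk profile. Section (iii.5) ties uptake to the study's own offers. RCT participants who have not completed vaccination "will be invited to take the SARS-CoV-2 antibody rapid test four times points during the study", namely at baseline and months 3, 6 and 9, and the fully vaccinated are also welcome to take it. The arms are to be compared on actual uptake.

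Section (iv) gives the model for the intervention effect: "Effectiveness of intervention will be examined by multivariable linear (for continuous nature of outcome) or Cox proportional hazard models (for binary outcome". The next sentence deals with drop-out: "Loss-to-follow-up will be reported and intention-to-treat analysis will be used for addressing the loss-to-follow"-up. Nothing defines the uptake event, the time origin, the censoring rule, or whether uptake means first uptake or uptake at each offer.

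Section (ii) plans 9 months of follow-up and settles on 294 workers "as a reasonable sample size with 147 subjects in each arm", a total that "has already taken into consideration a potential loss-to-follow-up rate of about 40"%. No loss rate is given by arm.

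**The concern.** Uptake differs from attitude in one respect. The attitude of a worker who has dropped out is unknown. For a test that the study itself offers at set times, a worker who no longer responds has most likely not taken the later offers, and no response is itself informative about uptake.

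A Cox model run in the usual way censors such a worker at last contact. It then assumes that later testing would have followed the rate seen in workers of the same arm who stayed. The hazard ratio compares acceptance among workers still in contact and is blind to how many workers each arm kept in contact.

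With about 40% loss planned, that matters if the arms lose workers at different rates. This is possible because the intervention arm receives the theory-based programme in addition to the general information given to controls. The trial could then report no effect on uptake while the proportion of randomised workers tested differs between arms, or report an effect larger or smaller than that difference.

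**Working it through.** **Plan's own figures.** The plan has no figure for uptake to reproduce. Its sample size is for willingness (a 20-point change, 90% power). The pooled two-sided 0.05 formula returns 124, 130, 124, 109 and 82 per arm, against 124, 130, 124, 109 and 79 stated; the unpooled formula returns 79 for the last. Used here from the documents: 147 per arm, three post-baseline offers, and about 40% loss, which is 147 × 0.4 ≈ 59 workers per arm if loss is equal.

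**Assumptions, not in the documents.** Acceptance *q* at each post-baseline offer among untested workers still in contact is the same in both arms. Cumulative loss *L* by month 9 is spread evenly over three intervals and is independent of acceptance. The baseline offer is left out at first.

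**Formulas.** Retention per interval is r = (1 − L)^(1/3).
- Proportion of randomised workers tested: U = q[r + r²(1 − q) + r³(1 − q)²].
- At every offer, tests divided by workers at risk equals q in each arm, whatever L is. With equal q the censored Cox hazard ratio is therefore 1.

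**Results for q = 0.25.**
- L = 30%: r = 0.8879, U = 0.25 × (0.8879 + 0.5913 + 0.3938) = 46.8%.
- L = 50%: r = 0.7937, U = 0.25 × (0.7937 + 0.4725 + 0.2813) = 38.7%.
- Difference: 8.1 points, with a hazard ratio of 1.
- L = 35% and 45%: 44.9% and 40.8%, a difference of 4.1 points, with a hazard ratio of 1.
- L = 40% in both arms: 42.9% in each, difference 0.

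**Range of the gap.**

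| Acceptance per offer | Loss 30% v 50% | Loss 35% v 45% |
|---|---|---|
| 15% | 5.6 points | 2.8 points |
| 25% | 8.1 points | 4.1 points |
| 40% | 10.4 points | 5.2 points |

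Including the baseline offer at 25% acceptance cuts the 30% v 50% gap from 8.1 to 6.1 points.

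**Precision.** For 46.8% v 38.7% with 147 per arm, the standard error is √(0.468 × 0.532/147 + 0.387 × 0.613/147) = 0.0575. The 95% half-width is 1.96 × 0.0575 ≈ 11.3 points, so the gap is smaller than the uncertainty around it.

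**Unequal acceptance.** Take 30% per offer in the intervention arm and 20% in control, with 600 simulated trials of 147 per arm.
- Loss 50% v 30% (intervention v control): expected proportions tested are 44.4% v 39.3%, while the censored hazard ratio is about 1.57.
- Loss 60% v 20%: 39.4% v 42.6%, while the censored hazard ratio is about 1.62.

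**Opposite check.** With equal acceptance of 20% and losses of 50% and 30%, counting lost workers as not tested gives 32.4% v 39.3%. A test of proportions reached p < 0.05 in about 22% to 25% of simulated trials, depending on which arm lost more, although acceptance was identical.

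**The case against.** The best defence is the sentence after the model: loss is to be handled by intention-to-treat. In a behavioural trial that can mean that lost workers count as not having done the behaviour. A reader might infer from the choice of Cox that the plan censors lost workers; the documents never say so. This part of the defence stands. But intention-to-treat fixes who is analysed and in which arm, not how a lost worker's uptake is coded, and a Cox model including everyone randomised still censors by default.

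Second, a reader might go further and say that uptake is known for every randomised worker. That is too strong. The kit is self-sampled, so one could be used after contact ends, and section (iii.1) also speaks of uptake of COVID-19 testing in general without excluding tests taken elsewhere. The narrower definition, a recorded study-offered test, is what section (iii.5) supports.

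Third, whether drop-out should count against uptake is a choice of estimand. Counting it does turn unrelated drop-out, such as a job change, into part of the arm difference, as the opposite check shows. This stands, and it is why a sensitivity analysis is needed.

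Fourth, a reader might infer that the planned analysis overstates uptake in both arms. With 40% loss and 25% acceptance, a survival curve would give 1 − 0.75³ = 57.8% against 42.9% of workers tested. But no survival estimate of uptake is planned, and a hazard ratio reports no level. Nor is a reversed direction a general result: in the cases worked it appeared only under the extreme 60% v 20% loss.

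**Conclusion.** The concern holds in a limited form. The plan assigns a model to binary outcomes but not the rule that decides what the model measures for uptake. Left at its default, that model would remove differential drop-out from the result. Under the stated assumptions the part removed is about 3 to 5 points for a 10-point difference in loss and about 6 to 10 points for a 20-point difference, and somewhat less if the baseline offer is included. It is zero if loss is equal.

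All of these gaps rest on assumed acceptance and assumed loss by arm. The documents do not show that loss will differ, nor that censoring is intended. The outcome is secondary, so the primary attitude comparison is not affected by this point. The change should still be made, because it replaces a method poorly matched to offers at fixed times with a simple one and can be settled before the data are seen.

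**What to change.** In section (iv), separate antibody-test uptake from the general rule for binary outcomes and state:
- Uptake is a recorded study-offered test at any post-baseline offer (months 3, 6 or 9), taken or not taken.
- Everyone randomised is in the denominator, in the assigned arm. No recorded test counts as not taken.
- The result is the difference in proportions with its 95% CI.
- A sensitivity analysis repeats the comparison among workers still in contact, or treats lost workers as missing. Loss by arm is reported next to it.

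Since section (iii.5) invites workers who have and have not completed vaccination, say that both are included; any split should use vaccination status at baseline.

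The cost is wording only, with no new data collection. The downsides are that reported uptake will be lower, kits used after contact is lost will be missed, and drop-out unrelated to testing can contribute to the difference. The sensitivity analysis and the loss figures let a reader judge that last part.
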